6.5.6 Chemistry and manufacturing

The components are synthesized under GMP by Farmitalia (Paromomycin) and by Schering (Gentamicin). Formulation of WR 279,396 was performed under GMP by the University of Iowa. Analysis of formulated WR 279,396 was within 6% of labeled paromomycin amount and 10% of labeled gentamicin amount (April 2002).

Formulation stability was determined over 8 weeks. At 45° C, there was a 48% decrement in paromomycin and a 36% decrement in gentamicin. At 35° C, there was a 17% decrement in paromomycin and a 9% decrement in gentamicin. At room temperature (19- 26° C), there was a 3% decrement in paromomycin and 2% decrement in gentamicin. Therefore, WR 279,396 must be stored at ~25° C or in the refrigerator (~5° C).

3MTegaderm is a product classified as a semipermeable adhesive BP and manufactured by 3M Health Care Ltd. 3M Tegaderm Absorbent Clear Acrylic Dressing is made of a unique construction that incorporates 3M Tegaderm Transparent Dressing as a top and a skin contact layer that sandwiches a proprietary acrylic polymer. Tegaderm is a sterile, waterproof, thin, transparent film dressing. It was designed to be applied over I.V. devices, clean skin, or wounds providing a breathable bacterial and viral barrier to outside contaminants. The dressing is available in a variety of sizes and shapes. 3M Tegaderm, which is permeable to both water vapor and oxygen, is impermeable to micro-organisms and once in position, it provides an effective barrier to external contamination, whilst producing a moist environment at the surface of the wound by reducing water vapor loss from the exposed tissue.

7.0 SUMMARY AND RATIONALE FOR THE PILOT PROOF OF CONCEPT PHASE 2 STUDY: 20 DAYS OF TREATMENTSTUDY WITH/WITHOUT OCCLUSION

A analysis of the data from the recent WR 279,396 study (HSRRB Log # A-97-68.1) indicates that by day 50, cure rate was 91.8% in the treatment group and 73.2% in controls ($x^2 = 5.60$, p= 0.017) and complete cure response was 95.8% among the former versus 75% among the latter ($x^2 = 8.04$, p= 0.004)

The Office of the Surgeon General, United States Army, represented by USAMMDA holds the IND for WR 279,396 (IND#50098) and will continue the development of the product through a commercial pharmaceutical partner with the goal of obtaining approval by the US FDA. If necessary, a Phase 3 study will be conducted with the new formulation of WR 279,396 in Paris and Tunis to start in October 2006.

Major questions remain to be addressed in order to accurately decide the appropriate arms of the pivotal Phase 3 study are: (a) is occlusion necessary and useful; and (b) would administration of WR 279,396 once-a-day for 20 days be as effective as twice a day for 20 days.

Any new treatment regimen in cutaneous leishmaniasis should be amenable to local health system constraints so our intent is to develop the simplest and shortest treatment schedule that will support easily application to children and soldiers in rural remote areas. A consistent difference of efficacy will be necessary to justify the relatively lower tolerance and higher cost of occlusive dressing. Decreasing the number of applications of the test drug will not only simplify the treatment but decrease the number of times that dressing is applied, thus diminishing the number of AEs triggered by peeling off the Tegaderm.

This study bridges the ongoing Phase 2 study that ended follow-up on November 2004 and the start of the Phase 3 trial.

8.0 EXPERIMENTAL PLAN

8.1 Trial Design

Fortyeight (48) patients of Old World cutaneous leishmaniasis will be randomly allocated to WR 279,396 treatment once-a-day for 20 days with occlusion (24 patients), without occlusion (24 patients). Patients not cured will be rescued with a conventional treatment accepted in Tunisia as determined by the primary care physician. The active ingredients of WR 279,396 are two aminoglycosides – paromomycin sulphate (15%) and gentamicin sulphate (0.5%) – in a base (AQIC).

Efficacy will be evaluated in terms of the number of lesions cured i.e. percentage of subjects cured at D50 (D1 is the first day of treatment) with no relapse during 3 months post-treatment follow-up. Cure is defined as 100% reepitheliazation without relapse by 3 months. Clinical improvement is defined as \geq 50% but \leq 100% reepitheliazation compared to pre-treatment lesion size at day 50 (\pm 7 days). Lack of clinical improvement at day 50 (\pm 7 days), relapse that is enlargement of the lesion compared to the previous measurement at any time after day 50 (\pm 7 days), or not demonstrating complete clinical response by 3 months will be a clinical failure. Time to cure will also be determined. Toxicity will be evaluated by local adverse reactions, and by laboratory signs of systemic events.

Induration of the lesion, as measured by the ball-pen technique, will be measured at the same time as lesion size. A photograph will be taken concurrently with these measurements to document the procedure and provide a visual record of the induration measurement and lesion size.

In addition to the clinical evaluation of the CL lesions, the following parameters/clinical healing surrogates will be investigated: (a) parasites loads will be determined in superficial and deep lesion dermis at D0 and D10. The mean parasite log-reduction ratio (log parasite load at D10/log parasite load at D0) in each group will be compared; (b) aminoglycoside concentrations in superficial and deep infiltrated dermis in each group will be compared.

One 4mm punch biopsy of the lesion randomized as explained above will be performed under epicutaneous plus transcutaneous anesthesia at day 0, and 4 mm punch biopsy at day 10. The biopsy specimen will be divided in two: superficial dermis and deep dermis. The following battery of tests will be performed on each homogenized tissue: (i) parasite load by the culture microtitration technique and/or other kind of parasite load quantification (the same technique will be used throughout the study) (ii) in situ aminoglycoside concentration will be determined using liquid chromatographic/mass spectrometric/mass spectrometric assay. The biopsy will be conducted by a qualified health professional under the supervision of a Medical Doctor in the health center. Past history of bleeding and hygiene conditions will be carefully considered, such as sampling environment conditions, and availability of local anti-bleeding drugs.

The results from this study will help determine the most efficient treatment regimen for the upcoming pivotal Phase 3 study and will answer questions that are crucial to improve the present treatment regimen with WR 279,396 of twice a day for 20 days. This will facilitate the management of patients in the field and will help answer FDA questions during the licensing phase of the product.

Risk for volunteers will be minimal (two punch biopsies under local anesthesia, performed by experienced clinicians).

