6.4 Clinical Efficacy of WR 279,396

6.4.1 Summary of Phase 2 studies

In 1999, a pilot phase 2 study was conducted in Colombia. This clinical study was a randomized, double blind trial of WR 279,396 compared to placebo (the cream base of WR 279,396), each administered twice-a-day for 20 days without occlusion.

In the active group in Colombia (in which WR 279,396 was applied without an occlusive dressing), 33 of 51 evaluable lesions cured (66%) at D50 and 5 lesions were non-evaluable (59% in intent-to-treat analysis). In the placebo group, 4 of 12 evaluable lesions cured (33%) at D50, and 5 lesions were non-evaluable.

There was no statistical difference between the pre-treatment sizes for cured vs failed lesions in WR 279396 patients (p = 0.7) nor in placebo patients (p = 0.8).

The 36 lesions that were treated with WR 279,396 were recognized as cured at the end of therapy on day 20 (20 lesions), at the first follow up on day 45 (13 lesions), and on day 90 (3 lesions). The 6 placebo lesions that cured were recognized on day 20 (1 lesion), day 45 (3 lesions), and day 90 (2 lesions). The mean cure time of 35 days for cured WR 279396 lesions was statistically different (p = 0.04) from the mean cure time of cured placebo lesions (56 days).

In 2003-2004, a Phase 2 study was conduced in Paris & Tunisia, Old World cutaneous leishmaniasis. 92 subjects were randomly assigned to treatment of which 90 subjects (80

from Tunisia and 10 from Paris) achieved all the follow-up period. Patients allocated treatment (n= 49) and placebo (n= 41) were similar for prognostic factors at inclusion (socio-demographic variables and clinical features of lesion). Each lesion was treated twice daily. Lesions were measured at the end of therapy, and at 50, 80 and 180 days after the institution of treatment. Cure rate at day 50 was 91.8% in the treatment group and 73.2% in controls ($x^2 = 5.60$, p= 0.017) and complete cure response was 95.8% among the former versus 75% among the latter ($x^2 = 8.04$, p= 0.004).

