8.12 Definition of responses using clinical criteria

Lesions will be measured in two perpendicular directions, and photographs will be taken, prior to therapy, at the end of therapy, and at 50 days, 3 months, (D1 being the first day of treatment). Physically identifying features if present will be hidden in photographs. Patients will be identified by initials and not by name. Because the trial can't be blinded, clinical evaluation at D50 will be performed by an independent physician ([name]) unaware of the occlusion process. Patients will be asked not to inform the evaluating physician if the lesion was covered.

Efficacy will be evaluated in terms of percentage of patients cured or improved at D50 (D1 is the first day of treatment) with no relapse during 3 months post-treatment follow-up.

1. Cure: 100% reepithelialization without relapse by 3

months.

2. Clinical improvement: $\geq 50\%$ but $\leq 100\%$ reepitheliazation compared to pre-

treatment lesion size at day 50 (\pm 7 days).

3. Clinical failure: a. Lack of clinical improvement at day 50 (\pm 7 days)

after the beginning of treatment.

b. Relapse that is enlargement of the lesion compared to the previous measurement at any time after day 50

 $(\pm 7 \text{ days}).$

c. Not demonstrating complete clinical response by 3

months (i.e. not being cured by 3 months).

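### The efficacy sentences require full healing at D50, but the cure and failure definitions allow until 3 months, so a lesion closing in between is a non-cure in one place and a cure in another

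*Protocol*

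**What the plan says.** **D50 as the deadline.** Section 8.1 evaluates efficacy as the "percentage of subjects cured at D50 (D1 is the first day of treatment) with no relapse during 3 months post-treatment follow-up". Section 8.4 repeats this, and 3.0 says the same of lesions. Under these sentences a lesion still open at D50 is not a success.

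**3 months as the deadline.** The next sentence of 8.1 reads "Cure is defined as 100% reepitheliazation without relapse by 3 months", with no D50 requirement; 8.12 gives the same definition. The last failure limb in 8.1 is "or not demonstrating complete clinical response by 3 months will be a clinical failure", and limb c in 8.12 explains this with the words "months (i.e. not being cured by 3 months". At D50 itself only "Lack of clinical improvement at day 50" is a failure (limb a), meaning less than 50% re-epithelialization.

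**No deadline, or a different standard.** Section 8.13, headed as the definition of cure, requires a complete clinical response and names no time. The efficacy sentence of 8.12 begins "Efficacy will be evaluated in terms of percentage of patients cured or improved at D50", and 9.2 likewise counts improved lesions as complete response at day 50.

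The timetable in 8.17 has two visits after treatment, at D50 and D90 (±7 days each). Closure after D50 is therefore first recorded at the last visit.

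**The concern.** The main outcome has two closure deadlines, and no passage says which one governs. The trial plans 20 (9.1) or 24 (3.0, 8.1) patients per arm, and 8.12 says it cannot be blinded. At that size, reclassifying one patient can move a Fisher test across its threshold, and the choice of deadline could be made after outcomes are known. The result is meant to inform the Phase 3 design (4.0, 8.1).

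**Working it through.** **1. Classifying patients under the text**

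| Lesion (no rescue) | Efficacy sentence, 8.1 and 8.4 | Cure definition, 8.12 | Failure limbs, 8.12 |
|---|---|---|---|
| 80% healed at D50, closed at last visit | not cured at D50 | cure | none applies |
| 40% healed at D50, closed at last visit | not cured at D50 | meets the wording of cure | failure under a |

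The 3-month limit in the cure line could be read as limiting relapse only. Limb c rules that out, because it makes 3 months the limit for being cured. If closure were already required at D50, limb c would have no work to do for a lesion that is improved but open at D50.

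**2. Which deadline the planning rate uses**

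Section 6.4.1 gives the Colombian active arm as 33 cures at D50 among 51 evaluable lesions plus 5 non-evaluable, so 56 in all. It times the 36 eventual cures as 20 at day 20, then "at the first follow up on day 45 (13 lesions), and on day 90 (3 lesions".

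- By D50: 20 + 13 = 33, and 33/56 = 58.9%.
- By day 90: 33 + 3 = 36, and 36/56 = 64.3%.

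The 60% in 9.1, attributed in its footnote to Colombia, matches the D50 count.

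**3. The plan's own sample size**

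Inputs from 9.1 and 9.2: 60% v 95% (35 read as percentage points), one-sided alpha 0.05, Fisher's exact test. Power is the sum of binomial probabilities over all tables with one-sided p ≤ 0.05. It is 77.8% at 19 per arm and 80.8% at 20, so the stated 20 reproduces. At 24 per arm it is 89.0%.

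**4. Illustration of a later deadline**

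Late-closure share on the 56-lesion base behind the 60%: 3/(56 − 33) = 3/23 = 13.0%. Applied to lesions open at D50 in both arms:

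- without occlusion: 0.60 + 0.40 × 3/23 = 65.2%
- with occlusion: 0.95 + 0.05 × 3/23 = 95.7%

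| One-sided Fisher power | 20 per arm | 24 per arm |
|---|---|---|
| D50 deadline, 60% v 95% | 81% | 89% |
| later deadline, 65.2% v 95.7% | 71% | 82% |

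Two checks on sensitivity:

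- Moving only the control rate, from 58.9% to 64.3% with 95% held, gives 82.8% to 71.1% at 20 per arm and 90.4% to 81.5% at 24.
- On evaluable lesions only, the late share is 3/(51 − 33) = 3/18 = 17%. That gives 66.7% v 95.8%, with power 68% at 20 per arm and 80% at 24.

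**5. How few patients matter**

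Hypothetical results at 24 per arm: 23 v 18 cures gives one-sided p = 0.049, and 23 v 19 gives p = 0.094. One control patient counted as a late cure changes the result.

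**The case against.** **The primary deadline is less open than it looks.** Every sentence that says how efficacy is evaluated (3.0, 8.1, 8.4, 8.12, 9.2) names D50; the 3-month limit sits in the cure and failure definitions. Under 9.2 as written, a lesion improved at D50 already responds, so its later closure changes nothing. This stands, and it lowers the severity. It does not remove the conflict: the efficacy sentences use the word cured, whose definition carries the other deadline, and the wording of 9.2 is itself at odds with 8.1. A statistical analysis plan could choose between the rules, but the contradictory definitions would remain in the protocol.

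**Meeting both cure and failure is uncommon.** Sections 3.0 and 8.1 provide rescue for patients not cured, and 8.14 removes failures who need re-treatment. Few lesions under 50% healed at D50 would reach the last visit unrescued. This stands.

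**A reader might infer that the later deadline shrinks the occlusion effect.** The documents do not establish that. The Colombian comparison with placebo rests on 12 evaluable placebo lesions, and this trial has no placebo arm. In the Paris and Tunisia study (6.4.1) the gap is 91.8 − 73.2 = 18.6 points for D50 cure and 95.8 − 75 = 20.8 points for complete cure response. The latter is neither defined nor timed, so it settles nothing, but it does not support shrinkage.

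**A reader might also infer a severe loss of power** by taking the lesions no longer active at day 105 in the earlier Tunisian trial (6.1.2) as a control cure rate. Section 6.1.2 does not equate inactive with fully re-epithelialized, and raising the control arm alone contradicts the premise that late closure occurs in both arms.

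**Conclusion.** The contradiction is real and lies in the operative definitions. It is clear for lesions 50% to 99% healed at D50 and closed at the last visit; the overlap of cure and failure for lesions under 50% is a lesser, uncommon case.

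D50 is the deadline that agrees with the rest of the plan. It matches the planning rate, and 8.12 specifies the assessor unaware of occlusion only for that visit. Section 18.0 mentions blinded tie-breaking assessment but names no visit.

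The size is moderate. With 13% late closure in both arms, power falls about 9 points at 20 per arm, below the planned 80%, and about 7 points at 24 per arm, staying above it. These figures assume that a New World late-closure share based on three lesions applies equally to both arms, that the 5 non-evaluable lesions did not close, and that the Fisher test is one-sided as in 9.1. The direction of any change in the estimated occlusion effect remains unknown. This should be fixed, but it does not by itself invalidate the design.

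**What to change.** Put one primary definition in 3.0, 8.1, 8.4, 8.12 (including its efficacy sentence), 8.13 and 9.2: success is 100% re-epithelialization at the D50 (±7 days) visit with no relapse through the final visit.

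- Call first closure after D50 a late cure: a non-success in the primary analysis, reported as a secondary endpoint.
- Reword the cure line and failure limb c so that the analysis categories are mutually exclusive.
- Settle the cured-or-improved wording in 8.12 and 9.2 in the same edit. If 9.2 is left as it is, it will contradict the new definition.
- Leave the rescue and withdrawal rules unchanged; only the analysis categories need editing.

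Cost: wording in six sections and one extra table, with no new data. Reported cure rates will be slightly lower because late closures no longer count.

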3.0 STUDY SUMMARY

Fortyeight patients (48) with Old World cutaneous leishmaniasis will be randomly allocated to WR 279,396 treatment once a day for 20 days with an optimized polyurethane dressing (occlusion) (24 patients), or without occlusion (24 patients). All

patients will be rescued with the standard of care accepted in Tunisia, if the patient is not cured. The active ingredients of WR 279,396 are two aminoglycosides – paromomycin sulphate (15%) and gentamicin sulphate (0.5%) – in a base (AQIC).

Efficacy will be evaluated in terms of the number of lesions cured at D50 (D1 is the first day of treatment) with no relapse during 3 months post-treatment follow-up. Cure is defined as 100% reepitheliazation without relapse by 3 months.

Tolerance will be evaluated by local adverse reactions and by laboratory signs of systemic events.

In addition to the clinical evaluation of the CL lesions, the following parameters/clinical healing surrogates will be investigated:

- (a) parasite load will be determined in superficial and deep lesional dermis samples at D0 and D10. The mean parasite reduction ratio (parasite load at D10/parasite load at D0) in each group will be compared;
- (b) aminoglycoside concentrations (paromomycin and gentmicin) in superficial and deep infiltrated dermis in each group will be compared

One 4mm punch biopsy of the lesion randomized as explained above will be performed under epicutaneous plus transcutaneous anesthesia at day 0 and one 4 mm punch biopsy at day 10. The biopsy specimen will be divided in two: superficial dermis and deep dermis.

The results from this study will help determine the most practical treatment schedule and will answer questions that are crucial to improve the present treatment regimen with WR 279,396 which is twice a day for 20 days. This will facilitate the management of patients in the field and will help answer FDA questions during the licensing phase of the product.

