distribution varies among the focuses. However, age distribution is skewed to young groups in the old foci and includes all age groups in the newly colonized ones.

Clinical characteristics: In a previous clinical trial, 75-80% of the lesions (all due to L. major) were at least partially ulcerative in nature and 17 to 20 % were either papules or nodules. Mean size of lesion at diagnosis was 23+/- 1.36 mm. Lesions were mainly located in uncovered parts of the body: legs: 41.4%, arms: 51.7%, trunk: 3.5% and face 3.5%. Few lesions had a rapid healing (6.9%) and 25.9% remained active until day 105. Direct smears originally positive at day 0 became negative among 56.4%, 71% and 92.3% in days 15, 45 and 105 respectively.

Epidemiology: The disease is now reemerging as an epidemic in rural areas in central Tunisia. We expect that patients will emerge from September to March with a peak in December. The medical team from Tunisia will screen approximately 10-15 patients at one time for entry into the study. Treatment and follow-up of the patients will be done on site (noted above). Members of the medical team will live in the study area until the end of the project.

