8.2 Trial endpoints

- 1. Primary endpoints: Lesion size and clinical response described as reepithelialization. Lesion size refers to ulcer size only, here, and the rest of the protocol.
- 2. Secondary endpoint: safety and tolerance of WR 279,396.
- 3. Third end point: D0 to D10 Deep Lesion Dermis Parasite Load Reduction Ratio.

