9.2 Efficacy calculations

Data analysis will be undertaken in 3 stages: conception of an electronic database from the questionnaire, data entry and cleaning to insure validity of data and statistical analysis: A database will be written from the CRF. Data entry with a double-check will be performed at the end of the protocol at the Tunisian site with U.S. support. Cleaning of the data base will be insured by comparing data entered to the computer to the information in the source documents. Data analysis will be done by an independent qualified statistician hired in the United States for this phase of the protocol.

The primary criterion for treatment evaluation will be the percentage of patients that demonstrate complete clinical response (all lesions cured or improved) at day 50. The response rate for WR 279,396 groups will be compared by Fisher's Exact test. Time for the ulcer to cure will also be determined and the means will be used to compare the two groups. Results will also be analyzed per cohort (Tegaderm VS no Tegaderm) and the age of the lesion at treatment D0 (\leq 2.5 months of age VS \geq 2.5 months of age).

The secondary efficacy calculation will be the deep lesional dermis parasite load log reduction ratio at Day 10 of treatment with/without occlusion. Mean parasite loads in the two groups, will be compared using student's t tests.

As for all efficacy calculations the data analysis for safety and tolerance of WR 279,396 will be done by a qualified statistician and results between the two groups compared.

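### The deep-dermis parasite endpoint has inconsistent definitions, and the one in 8.1, a quotient of two logs, mixes baseline load and unit with parasite kill

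*Protocol*

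**What the plan says.** Four sections of the protocol describe this endpoint.

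- Section 3.0 gives the untransformed ratio: "The mean parasite reduction ratio (parasite load at D10/parasite load at D0) in each group will be compared".
- Section 8.1 divides one log by another: "The mean parasite log-reduction ratio (log parasite load at D10/log parasite load at D0) in each group will be compared".
- Section 8.2 lists it as the third endpoint, after safety and tolerance, with no log and no formula: "D0 to D10 Deep Lesion Dermis Parasite Load Reduction Ratio".
- Section 9.2 ranks it higher and calls it a log ratio: "The secondary efficacy calculation will be the deep lesional dermis parasite load log reduction ratio at Day 10 of treatment with/without occlusion". The next sentence names a different quantity for the test: "Mean parasite loads in the two groups, will be compared using student's t tests".

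Sections 3.0 and 8.1 cover superficial and deep dermis; 8.2 and 9.2 name deep dermis only. On the assay, 8.1 says "parasite load by the culture microtitration technique and/or other kind of parasite load quantification (the same technique will be used throughout the study", and the timetable in 8.17 lists both culture microdilution and DNA/RNA methods. No load unit or detection limit is stated.

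**The concern.** The raw ratio, the quotient of logs and the mean load are different quantities. They can rank patients differently and lead to different conclusions, and an analyst could choose among them after seeing the data. A separate analysis plan could add detail, but it would have to contradict at least one section of the protocol.

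The 8.1 formula also has a fault of its own. A log reduction is a difference of logs, log(D10) − log(D0), which equals log(D10/D0). Dividing the logs gives a number that depends on the starting load and on the unit as well as on the kill.

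Section 2.0 expects the surrogates to help settle the number and duration of treatments, and every patient has two punch biopsies, partly for this measure.

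**Working it through.** The protocol gives no load, SD, effect size or power for this endpoint, so there is no stated figure to reproduce. Steps 1 to 3 are algebra and need no assumptions about variability. Steps 4 and 5 are simulations with assumed inputs and the 24 patients per arm of section 8.1.

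**1. Equal kill, different value.** Take a 100-fold kill, so D10/D0 = 0.01 and log10(D0) − log10(D10) = 2.0 in every row.

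| D0 | D10 | log10(D10)/log10(D0) |
|---|---|---|
| 10^6 | 10^4 | 4/6 = 0.67 |
| 10^4 | 10^2 | 2/4 = 0.50 |
| 10^3 | 10^1 | 1/3 = 0.33 |
| 10^2 | 10^0 | 0/2 = 0 |
| 10^1 | 10^−1 | −1/1 = −1 |

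Conversely, a quotient of 0.5 means a 1,000-fold kill from 10^6, a 100-fold kill from 10^4 and a 10-fold kill from 10^2.

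**2. Unit.** A unit 1,000 times larger adds 3 to each log. The first row becomes 7/9 = 0.78 and the third 4/6 = 0.67. The order of two patients can reverse. Patient A goes from 10^5 to 10^3 (2.0 logs) and patient B from 10^3 to 10^1.5 (1.5 logs). Per mg the quotients are 3/5 = 0.60 and 1.5/3 = 0.50, so B looks better. Per kg (6 added to each log) they are 9/11 = 0.818 and 7.5/9 = 0.833, so A looks better. The base of the log does not matter.

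**3. Baseline near 1 unit.** The denominator log10(D0) passes through zero at D0 = 1. A 100-fold kill from D0 = 2, 1.1 or 0.5 gives −5.6, −47.3 or +7.6.

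**4. False positives.** Assumed: a true 2-log kill in both arms, SD 0.7 log for baseline and for change, two-sided 5% t-test.

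| Baseline means (log10) | Quotient of logs rejects | Log difference rejects |
|---|---|---|
| 4 v 4 | about 5% | about 5% |
| 4.5 v 4 | about 17–18% | about 5% |
| 5 v 4 | about 52% | about 5% |

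Adding 3 logs to both arms by a unit change alone lowers the last quotient figure from about 52% to about 24%. For scale, with SD 0.7 the standard error of the baseline difference is 0.7 × √(2/24) = 0.20. A chance imbalance of 0.5 log or more is then about 2.5 standard errors, or roughly 1.3% of randomisations. The 17–18% is therefore a rate given such an imbalance, not an overall error rate.

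**5. Power.** Assumed: mean kill 1.5 v 2.2 log, SD 0.8, two-sided 5%.

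| Baseline mean, SD (log10) | Quotient of logs | Log difference |
|---|---|---|
| 4, 1.2 | 52% | 84% |
| 4, 0.7 | 76% | 84% |
| 6, 1.2 | 74% | 86% |
| 6, 0.7 | 81% | 84% |
| 4, 1.2; D10 floored at 1 unit | 63% | 81% |
| 4, 1.2; D10 floored at 0.5 log | 69% | 78% |
| Kill proportional to baseline log load | about 85% | about 66% |

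Repeat runs differ by a point or two. Leaving out the last row, the range over all runs is about 52–83% against 78–86%. In the first case a 1,000-fold unit change moves the quotient's power from about 51% to about 75% and leaves the log difference unchanged. The raw ratio of 3.0 has about 35% power in that case. A literal t-test of untransformed D10 loads has about 3–14% across the cases.

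**The case against.** **Loose wording.** Section 8.1 may mean log(D10/D0). If so, the unit and baseline problems disappear. But the text divides one log by the other, nothing elsewhere corrects it, and the conflict with 3.0 and with the tested quantity in 9.2 would remain.

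**Section 9.2.** Its second sentence may be shorthand for testing the log reduction ratio named just before it. That is a fair reading. A reader might infer that the plan discards the D0 biopsy and compares D10 loads only, but the text does not say so. The 3–14% power applies only to the literal reading. The firm conflict of formulas is between 3.0 and 8.1.

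**The quotient still measures kill.** A reader might infer that it reflects baseline and unit instead of kill. That is wrong: for a given baseline above 1 unit it falls as kill rises, and it detects a real difference with reasonable power in several cases above. Nor is there a general inflation of false positives. Allocation is 1:1 at random, and with balanced baselines the test holds its level.

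**One technique throughout.** Section 8.1 fixes this, so units should not differ between patients or arms. That stands. What remains is a result on an arbitrary scale.

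**Power.** Quoting only the worst case, 52% against 84%, would mislead. All inputs are assumed, and the order reverses if kill is proportional to baseline log load.

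**Undetectable loads.** Section 6.1.2 reports that smears positive at day 0 in an earlier trial "became negative among 56.4%, 71% and 92.3% in days 15, 45 and 105 respectively". This is indirect evidence, from smears, that undetectable D10 loads may be common. But log(0) is undefined for the log difference too, so this does not separate the two measures, and a rule for it could sit in an analysis plan that is not shown.

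**Conclusion.** The point holds as an inconsistency of definition together with one badly chosen formula. The algebra is certain for 8.1 as written: equal 100-fold kills give 0.67 or 0.33 depending on baseline, the values move with the unit, and they become unstable when D0 is near 1 unit. The main cost is to interpretation and, under most of the inputs tried, to power. The exposure to false positives is conditional: about 17–18% if arm baselines happen to differ by 0.5 log, at SDs of 0.7, and near 5% otherwise. The size of the power loss cannot be fixed from the protocol.

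The rank is also unsettled: third in 8.2, secondary efficacy in 9.2. A reader might infer that the main efficacy result is at risk. It is not: this is a surrogate, and the cure comparison does not use it. The change is worth making because the protocol itself fixes the endpoint in incompatible ways.

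**What to change.** 1. In 3.0, 8.1, 8.2 and 9.2, define the endpoint once as log10(D0) − log10(D10) in deep dermis. This value does not depend on the unit, and a 100-fold kill is 2.0 at every baseline.
2. Give it the same rank in 8.2 and 9.2.
3. In 9.2, state that the between-arm test is applied to this log10 reduction. A t-test is adequate. ANCOVA adjusted for baseline log10 load is equally acceptable and is a matter of preference; in the first power case above the two have nearly the same power (82–84%).
4. State that undetectable loads take a value fixed in advance from the assay limit. The detail can go in the analysis plan.

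The cost is a wording amendment and trivial analysis work. No samples, visits or patients are added.
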